10.3.2 The role of the investigator

The investigator must **assess the seriousness of each adverse event** and record all serious and non-serious adverse events in the case report form (CRF).

The investigator must **document** serious adverse events **as thoroughly as possible** and provide a definitive medical diagnosis, if possible.

The investigator must **assess the intensity** of the adverse events:

- by using the CTCAE scale

The investigator must **assess the causal relationship** between serious adverse events and the investigational strategy added by the study.

The method used by the investigator is based on the WHO Uppsala Monitoring Centre method and uses the following 4 causality terms:

- Certain
- Probable/likely
- Possible
- Unlikely (not excluded)

Their definition is presented in the following table (excerpt from WHO-UMC causality categories, version dated 17/04/2012).

Table: WHO-UMC causality categories (excerpt)

Causality term	Assessment criteria*
Certain to occur	
 • Event or laboratory test abnormality, with plausible time relationship to drug intake** • Cannot be explained by disease or other drugs • Response to withdrawal plausible (pharmacologically, pathologically) • Event definitive pharmacologically or phenomenologically (i.e. an objective and specific medical disorder or a recognized pharmacological phenomenon) • Rechallenge satisfactory, if necessary
Probable/Likely	
 • Event or laboratory test abnormality, with reasonable time relationship to drug intake** • Unlikely to be attributed to disease or other drugs • Response to withdrawal clinically reasonable • Rechallenge not required
Possible	
 • Event or laboratory test abnormality, with reasonable time relationship to drug intake** • Could also be explained by disease or other drugs • Information on drug withdrawal may be lacking or unclear
Unlikely	
 • Event or laboratory test abnormality, with a time to drug intake** that makes a relationship improbable (but not impossible) • Disease or other drugs provide plausible explanations

*All points should be reasonably complied with

**Or study procedures

10.3.2.1 Serious adverse events that require the investigator to notify the sponsor without delay

As per article R.1123-49 of the *Code de la Santé Publique* (French Public Health Code), the investigator notifies the sponsor without delay on the day the investigator becomes aware of any serious adverse event which occurs during a study that meets the description in line 1° of Article L.1121-1 of the Code de la Santé Publique, **with the exception of any event which is listed in the protocol** and, if applicable, in the investigator's brochure as not requiring notification.

A serious adverse event is any untoward medical occurrence that:

- 1- results in death
- 2- is life-threatening to the participant enrolled in the study (for this protocol, see exceptions listed on paragraph 10.3.2.2.2)
- 3- requires hospitalization or prolongation of existing hospitalization (see exceptions listed on paragraph 10.3.2.2.2)
- 4- results in persistent or significant disability/incapacity
- 5- is a congenital anomaly/birth defect

10.3.2.2 Specific features of the protocol

10.3.2.2.1 Other events that require the investigator to notify without delay the sponsor

- Adverse events deemed “medically significant”

The investigator must notify the sponsor without delay on the day the investigator becomes aware of these adverse events, in the same manner and within the same deadline as for serious adverse events (see above).

- acute heart failure grade 4 and 5 according to CTCAE scale (not related to COVID 19)
- myocardial infarction grade 4 and 5 according to CTCAE scale,
- myocarditis grade 4 and 5 according to CTCAE scale,
- cardiogenic shock with requirement of vasopressors or a circulatory assistance (not related to COVID 19 according to investigator),
- stroke 4 and 5 according to CTCAE scale,
- Hypertension grade 4 and 5 according to CTCAE scale.
- Acute Kidney Injury, requiring renal replacement therapy, grade 4 and 5 according to CTCAE scale

Grade 4 correspond to life threatening and grade 5 correspond to fatal outcome

- ***In utero exposure***

The investigator must notify the sponsor without delay on the day the investigator becomes aware of any pregnancy that occurs during the study, even if it is not associated with an adverse event.

If the investigational medicinal product is genotoxic, every case of maternal or paternal exposure must be notified.

- Exposure **while breastfeeding**

Exposure while breastfeeding occurs if an infant or a child may have been exposed to a medicinal product *via* the breast milk of a mother being treated with an investigational medicinal product.

Even if it is not associated with an adverse event, the investigator must notify the sponsor without delay on the day the investigator becomes aware of the exposure while breastfeeding.

10.3.2.2 Serious adverse events that do not require the investigator to notify the sponsor without delay

These serious adverse events are only recorded in the case report forms (CRF).

- *Normal and natural course of the condition:*
 - **Re-Hospitalisation** for any reason (including CV reasons) except those described in the Adverse events deemed “medically significant” paragraph
 - **Admission to an intensive-care unit** except those described in the Adverse events deemed “medically significant” paragraph
 - **Acute cardiac injury:** acute heart failure, type 1 or 2 myocardial infarction, myocarditis, except those described in the Adverse events deemed “medically significant” paragraph
 - **Acute kidney injury**, except grade 4 and 5 according CTCAE scale or requiring renal replacement therapy
 - **Acute respiratory distress syndrome**, requirement of mechanical ventilation (invasive or not) or an ECMO
 - **Multiple organ failure** except grade 5 according CTCAE scale.

The primary objective of the study is to compare the effect of discontinuation versus continuation of RAS blockers on the clinical course of patients with confirmed COVID-19 infection leading to hospitalization

The mortality rate linked to the studied condition of COVID-19 is 22% at 28 day (3).

The interventions added by the study being Continuation or Discontinuation of RAS blockers in context of pandemic of COVID-19, all serious adverse event ≤ grade “3 (and except those described in the Adverse events deemed “medically significant” paragraph) do not need to be notified to the sponsor without delay but will be recorded in the case report forms.

Retrieval of all serious adverse event from the case report forms will be carried out by clinical research unit as often as necessary.

The retrieval of all serious adverse event data will be sent by the clinical research unit to the vigilance department at [contact] and to the members of the Data Safety Monitoring Board before each meeting of the DSMB.

If there is any discrepancy between the groups or if the mortality rate is higher than expected, affecting participants safety and which require the sponsor to take urgent safety measures, the ANSM (French Health Products Safety Agency) will be informed about the emerging safety issue without delay.

- *Special circumstances*
 - **Hospitalisation** for a known pathology
 - **Hospitalisation** for medical treatment or surgery scheduled before the research

All serious adverse reaction described in the SMPC of the treatments (RAS blockers, Calcium Chanel blocker, other antihypertensive drug (non-RAS blockers), diuretics and nitrates (oral or IV) **do not need to be notified to the sponsor without delay but will be recorded in the case report forms.**

The investigator must report these adverse reactions to the relevant regional pharmacovigilance center, Centre Régional de Pharmacovigilance (CRPV).

Common side effects associated with RAS blockers (which could be serious) include:

- hyperkalemia
- headaches, dizziness
- hypotension, syncope
- irritative cough, bronchitis, sinusitis, dyspnea
- digestive disorders, abdominal discomfort, dyspepsia, diarrhea, nausea and vomiting
- rash
- muscular spasms
- fatigue, chest pain

Less common side effects include:

- neutropenia, agranulocytosis, anemia, thrombopenia
- confusion
- tremor, vertigo
- conjunctivitis
- tinnitus, hearing disorder
- vascular stenosis, vasculitis
- glossitis
- cholestatic jaundice
- exfoliative dermatitis
- asthenia

10.3.2.3 Period during which SAEs must be notified without delay by the investigator to the sponsor

The investigator must notify the sponsor without delay of any serious adverse events as defined in the corresponding section:

- from the date on which the participant signs the consent form
- throughout the whole follow-up period required for the trial 28 days \pm 4 days

- indefinitely, if the SAE is likely to be due to the investigational medicinal product or to the study interventions (e.g. serious reactions that could appear long after exposure to the medication, such as cancers or congenital abnormalities)

10.3.2.4 Procedures and deadlines for notifying the sponsor

The initial notification of an SAE must be provided in a written report signed by the investigator using a SAE notification form specific to the study and intended for this purpose (in the case report form).

Each item in this form must be completed by the investigator so that the sponsor can carry out the appropriate analysis.

The initial notification to the sponsor of a serious adverse event must be quickly followed by an additional detailed written report (or reports) so that the case outcome may be monitored by the Safety Department or to provide further information.

Whenever possible, the investigator will provide the sponsor with any documents that may be useful (medical reports, laboratory test results, results from additional examinations, etc.). These documents must be non-identifying. In addition, the documents must include the following: study acronym, number and participant's initials.

Any adverse event will be monitored until fully resolved (stabilization at a level considered acceptable by the investigator or return to the previous state) even if the participant has left the study.

The initial notification, the SAE follow-up reports and all other documents must be sent to the sponsor's Safety Department by email ([contact]). It should be noted that it is possible to send SAE reports to the Safety Department by fax to [name] only in the event of a failed attempt to send the SAE report by email (in order to avoid duplication).

The investigator must respond to all requests from the sponsor for additional information. For all questions relating to the notification of an adverse event, the Safety Department can be contacted via email: [contact].

10.3.3 Role of the sponsor

The sponsor, represented by its Safety Department, shall continuously, throughout the trial, assess the safety of each investigational medicinal product throughout the study.

10.3.3.1 Analysis and declaration of serious adverse events

The sponsor assesses:

- the **seriousness** of all the adverse events reported
- the **causal relationship** between these events and each investigational medical procedure added by the study and any other treatments,

All serious adverse events which the investigator and/or the sponsor reasonably believe may have a causal relationship with the investigational medicinal product are classed as suspected serious adverse reactions.

- the **expected or unexpected nature** of the serious adverse reactions

Any serious adverse reaction whose nature, severity, frequency or outcome is inconsistent with the safety information described in the summary of product characteristics, or in the investigator's brochure if the product is not authorized, is considered unexpected.

The sponsor, represented by its Safety Department, assesses the expected/unexpected nature of a serious adverse reaction based on the information described below.

- ❖ For serious adverse events likely to be related to the investigational product(s): RAS blockers
 - refer to the SmPC of the used products, in force at the time of SAE receipt.
- ❖ The serious adverse events potentially related to the interventions, specific to the study are, and related to discontinuation of RAS blockers:
 - Increase of cardiovascular events, such as acute heart failure, uncontrolled hypertension, myocardial infarction or stroke, myocarditis, cardiogenic shock with requirement of vasopressors or a circulatory assistance,
 - More COVID-19 related cardiac injuries, such as acute cardiac injury or myocarditis
 - More acute lung injuries

The sponsor will report all suspected unexpected serious adverse reactions (SUSARs), within the regulatory time frame, to the ANSM:

- The sponsor must send the initial report without delay upon learning of the unexpected serious adverse reaction if is fatal or life-threatening, or otherwise within 15 days from learning of any other type of unexpected serious adverse reaction;
- All additional, relevant information must be declared by the sponsor in the form of follow-up reports within a period of 8 calendar days starting from when the sponsor had this information.

Any suspected unexpected serious adverse reaction must also be declared electronically using the Eudravigilance European adverse drug reactions database managed by the European Medicines Agency (EMA).

The sponsor must notify all the investigators involved about any information that could adversely affect the safety of the research participants.

10.3.3.2 Analysis and declaration of other safety data

This means any new information that prompts a reassessment of the risk/benefit ratio of the trial or of the product under investigation, or which could be sufficient to consider changes to the use of the product, the trial procedures or trial documentation, or the suspension, cancellation or amendment of the research trial or of other similar trials. For trials involving the first administration or use of a health product in healthy volunteers: any serious adverse reaction.

The sponsor will inform the competent authority and the Research Ethics Committee without delay upon knowledge of any emerging safety issue and, if applicable, describe what measures have been taken.

Following the initial declaration of any emerging safety issue, the sponsor will address to competent authorities any additional relevant information about the emerging safety issue in the form of a follow-up report, which must be sent no later than 8 days after learning of the information.

10.3.3.3 Annual safety report

Special case of short-term clinical trials:

If the duration of the clinical trial is less than one year, the promoter does not have to establish an annual safety report.

However, if several short-term clinical trials have been carried out during this same period, it is recommended to submit an annual safety report to the Member States concerned, which allows an evaluation of comprehensive information on the safety of the investigational medicinal product.

10.3.4 Data Safety Monitoring Board (DSMB)

The Data Safety Monitoring Board (DSMB) may be established by the sponsor. Its primary mission is to monitor safety data. It can have other missions, such as monitoring efficacy data (especially if the protocol includes interim analyses).

The sponsor is responsible for justifying the creation or absence of such a committee to the Competent Authority (ANSM) and to the CPP (Research Ethics Committee).

A DSMB will be established for this trial. The DSMB must hold its first meeting before the first participant is enrolled and ideally before the protocol is submitted to the competent authority and the CPP (Research Ethics Committee).

All missions as well as the specific operating procedures of the DSMB are described in the study's DSMB charter.

The DSMB members are:

- List the members of the DSMB → Pr [name] (cardiology, CHU Nîmes), Pr [name] (intensive-care medicine, Pitié-Salpêtrière hospital, Paris), [name] (clinical pharmacology, Hospices Civils, Lyon)

The DSMB will operate in accordance with the sponsor's procedures. The DSMB works in an advisory capacity only and the sponsor retains all decision-making authority.

11 DATA MANAGEMENT

11.1 Data collection procedures

All information required by the protocol must be provided in the case report form and given by the investigator for each missing explanation. The data will be transferred in the case report form as and when they are obtained.

11.2 Identification of data recorded directly in the CRFs which will be considered as source data

All data will be recorded first in the medical file.

11.3 Right to access data and source documents

11.3.1 Data access

In accordance with GCPs:

- the sponsor is responsible for ensuring all parties involved in the study agree to guarantee direct access to all locations where the study will be carried out, the source data, the source documents and the reports, for the purposes of the sponsor's quality control and audit procedures or inspections by the competent authority
- the investigators will ensure the persons in charge of monitoring, quality control and auditing or inspecting the interventional study involving human participants have access to the documents and personal data strictly necessary for these tasks, in accordance with the statutory and regulatory provisions in force (Articles L.1121-3 and R.5121-13 of the French Public Health Code)

11.3.2 Source documents

Source documents are defined as any original document or item that can prove the existence or accuracy of a data or a fact recorded during the study. These documents will be kept in accordance with the regulations in force by the investigator or by the hospital in the case of a hospital medical file (the medical file contains original biological examination results, summary from imaging examinations, etc.)

11.3.3 Data confidentiality

The persons responsible for the quality control of clinical studies (Article L.1121-3 of the *Code de la Santé Publique* [French Public Health Code]) will take all necessary precautions to ensure the confidentiality of information relating to the investigational medicinal products, the study, the study participants and in particular their identity and the results obtained.

These persons, as well as the investigators themselves, are bound by professional secrecy (in accordance with the conditions set out in Articles 226-13 and 226-14 of the *Code Pénal* [French Criminal Code]).

During and after the research involving human participants, all data collected concerning the participants and sent to the sponsor by the investigators (or any other specialized collaborators) will be rendered non-identifying.

Under no circumstances shall the names and addresses of the participants involved be shown. Only the participant's initials will be recorded, accompanied by an encoded number specific to the study indicating the order of enrolment.

The sponsor will ensure that each participant has given written permission for any personal information about him or her which is strictly necessary for the quality control of the study to be accessed.

11.4 Data processing and storage of research documents and data

11.4.1 Identification of the data processing manager and location(s)

All subject data generated during the study will be recorded in a paper CRF.

Only the investigator and co-workers authorized by him (as listed on the specific form provided by the Sponsor) will be allowed to enter data or to make corrections in the paper CRF. At the end of the study each eCRF will be signed and dated by the investigator and archived.

During the study, all data will be recorded by a central team from paper CRF in the electronic Case Report Form (eCRF) provided by the Sponsor: web-based electronic support. eCRF will be specifically designed to meet the data recording requirements of the Clinical Study Protocol.

Statistical analysis will be conducted by Unité de Recherche Clinique Lariboisière-Saint Louis under the responsibility of Pr [name].

11.4.2 Data entry

Data entry will be performed by investigators and co-workers authorized by him by specially trained staff in non-identifying case report forms.

11.5 Data ownership

AP-HP is the owner of the data. The data cannot be used or disclosed to a third party without its prior permission.

12 STATISTICAL ASPECTS

12.1 Statistical Design / Model

ACORES-2 will be a phase III national, multicenter, comparative, controlled, randomized, open label trial in parallel groups among patients hospitalized for COVID-19 and treated with RAS blockers. It will test the superiority of the "discontinuation strategy" versus the "continuation strategy". Participants will be distributed in a 1:1 ratio between the 2 groups.

12.2 Null and Alternative Hypotheses

The primary aim of the trial is to demonstrate difference in time to clinical improvement (T) between discontinuation strategy vs the “continuation strategy”

The null and alternative hypotheses are as follows:

$H_0: T_{\text{discontinuation}} = T_{\text{continuation}}$

versus

$H_1: T_{\text{discontinuation}} \neq T_{\text{continuation}}$

12.3 Planned Analyses

12.3.1 Populations to be analysed

The main analysis will be based on the intent-to-treat population (ITT) of all patients randomised (irrespective of which study treatment is given or if any study treatment is adequately received). Per protocol analysis (PP) of all patients randomized & treated without major protocol violations/deviations will be considered as secondary.

12.3.2 Patient accountability

Disposition of patients, patient status and patients excluded from PP populations will be summarised by treatment group. Descriptive statistics for primary reason for patient’s withdrawal will be also presented by treatment group as well as a list of these patients sorted by treatment group.

Reasons for drop-outs in each treatment group will be displayed. A detailed list of drop-out patients will also be provided.

12.3.3 Baseline characteristics

Baseline characteristics will be tabulated and comparability / differences between the treatment groups will be examined by means of descriptive statistics. As recommended by CONSORT no tests will be carried on baseline variables.

12.3.4 Interim analyses

Interim analyses will be carried out after 33% and 66% of inclusion. They will allow early rejection of the null hypothesis for efficacy. We will use the O'Brien-Fleming spending function to determine the test boundaries. In addition a blinded sample size reassessment procedure will be performed at the second interim analysis that would allow the data safety monitoring board to recommend, if required, an increase of the sample size to reach the expected power.

12.4 Efficacy Analysis

12.4.1 Main Efficacy Criterion

The primary ITT analysis on the primary endpoint will be carried out by Cox model of survival analysis. Possible interaction between treatment and strata will be tested. The corresponding 95% confidence interval of Hazard ratio will be calculated from Cox model.

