4.2.2 Number of participating sites

We are expecting to enroll 554 patients (277 in each arm) in 12 French centers.

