12.8 Sample size issues

This trial is designed in a public health emergency context, at which time there is limited information about clinical outcomes in Covid-19 hospitalized patients.

We will include $n=277$ patients in each group to provide the trial with 90% power to detect a difference, at a two-sided global significance level of $\alpha = 0.05$, of 5 days in the median time to clinical improvement between the two groups, assuming that the median time in the standard-care group will be 16 days (B. Cao et al NEJM March 18th 2020). We considered 3 equally spaced analyses allowing early stopping for efficacy according to the O'Brien-Fleming boundaries.

Considering around 25 % of patients in the cardiac insufficiency stratum, we also checked that, in case of significant interaction between stratum and treatment due to a minor effect of the treatment in patients with cardiac insufficiency, this sample size will also allow 80% to detect a 5 days in the median time to clinical improvement in the other stratum that will include $n=207$ patients/group.

Primary efficacy analysis will be on an intention-to-treat basis and included all the patients who had undergone randomization.

The time to clinical improvement will be assessed after day 28, and absence of clinical improvement or death before day 28 will be considered as right-censored at day 28.

The time to clinical improvement will be analyzed by Kaplan-Meier method and compared with a log-rank test.

In addition a blinded sample size reassessment procedure will be performed at the second interim analysis that would allow the data safety monitoring board to recommend, if required, an increase of the sample size to reach the expected power.

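### The primary 95% Cox confidence interval does not match the three-look O'Brien-Fleming test: coverage is slightly low, it can disagree with the test, and the hazard ratio is overstated after an early stop

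*Protocol*

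**What the plan says.** Section 12.3.4 plans interim analyses after 33% and 66% of inclusions, which may reject the null hypothesis early for efficacy, and it uses the O'Brien-Fleming "spending function to determine the test boundaries". Section 12.8 agrees: "We considered 3 equally spaced analyses allowing early stopping for efficacy according to the O'Brien-Fleming boundaries". The same section sets a two-sided global level of 0.05 and sizes the trial "to provide the trial with 90% power to detect a difference" "of 5 days in the median time to clinical improvement between the two groups".

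For the estimate, section 12.4.1 names the Cox model and then says: "The corresponding 95% confidence interval of Hazard ratio will be calculated from Cox model". It does not mention the interim looks or a confidence level tied to the boundary.

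Section 12.4.2 opens the hierarchy of secondary criteria only if the main criterion differs significantly. It does not say whether that is read from the boundary or from the interval.

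**The concern.** With early looks for efficacy and a global level of 0.05, the last look must be tested at a nominal level below 0.05. A 95% interval from a Cox model, read plainly, is the estimate plus or minus 1.96 standard errors, which belongs to a single test at 0.05.

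This has three consequences:
- The interval covers the true value slightly less often than 95%.
- At the final look it can exclude 1 although the test has failed. The report would then carry two conflicting messages, and a reader could take the gate to the secondary criteria as open.
- The Cox hazard ratio is reported without correction after an early stop, and crossing an early boundary selects large estimates.

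**Working it through.** **Inputs.** From the protocol: two-sided global level 0.05, three equally spaced efficacy looks, 90% power (sections 12.3.4 and 12.8). Assumptions: information is proportional to inclusions (fractions 1/3, 2/3, 1), and the Cox and log-rank statistics are treated as equal. The protocol gives no numerical boundaries, and its two sections can be read as the spending function or as the classical O'Brien-Fleming bounds, so both are shown.

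**Boundaries.**

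| Look | Spending function, critical abs(z) | Classical, critical abs(z) |
|---|---|---|
| 1 | 3.710 | 3.471 |
| 2 | 2.511 | 2.454 |
| 3 | 1.993 | 2.004 |
| Final nominal p | 0.0463 | 0.0451 |

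Both sets reproduce the plan's global level: simulated rejection under the null is 4.97% and 4.99%. With exact fractions of 33% and 66% the final spending-function value is 1.992, so nothing changes.

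**Interval matched to the final critical value.** Its level is 1 − 0.0463 = 95.4% or 1 − 0.0451 = 95.5%. Its width relative to the ordinary interval is 1.993/1.960 = 1.017 or 2.004/1.960 = 1.022.

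**Where interval and test disagree.** This happens at the final look when |z| lies between 1.960 and the critical value. The estimated hazard ratio at a given z is exp(z/√(D/4)) for D events. The protocol states no event count, so D is an assumption:
- D = 424. This is 554 × 0.766, the exponential 28-day event share with medians of 16 and 11 days. Then √(D/4) = 10.30, and the disagreement strip runs from 1.2096 to 1.2135 (spending) or 1.2148 (classical).
- D = 300. This is 4(1.96 + 1.282)²/(ln(16/11))², rounded up, the events needed for 90% power at one look. Then √(D/4) = 8.66, and the strip runs from 1.254 to 1.259 or 1.260.

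Reciprocal strips lie below 1. The probability of disagreement is 0.3 to 0.5% under the null, 0.5 to 0.7% at the 90%-power effect, and at most 1.2% (spending) or 1.6% (classical).

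**Behaviour of the ordinary interval.** Two million simulated trials per setting, with drift 3.27 for 90% power:

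| Quantity | Spending | Classical |
|---|---|---|
| Overall coverage at 90% power | 93.5% | 93.8% |
| Lowest coverage between null and design effect | 93.4% | 93.4% |
| Coverage under the null | 94.6 to 94.7% | 94.5% |
| Stop at look 1 / look 2 | 3.4% / 52.9% | 5.7% / 53.0% |
| Coverage given a stop at look 2 | 97.2% | 97.8% |
| Mean log hazard ratio over truth, look 2 | 1.24 | 1.22 |
| Same, any early stop | 1.30 | 1.30 |
| Same, all trials | 1.07 | 1.08 |

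Stops by look 2 add up to 3.4 + 52.9 = 56.3% and 5.7 + 53.0 = 58.7%.

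If the trial really had 424 events at a hazard ratio of 16/11, power would be about 97%. Overall coverage would then be 94.0 to 94.3%, and early-stop inflation 18 to 19%. (Under the same exponential assumption, 90% power needs about 199 to 204 per arm rather than 277. That is a separate matter and does not affect this point.)

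**What the candidate intervals change.**
- Stagewise ordering, look 1: identical to the ordinary interval.
- Stagewise ordering, look 2: 0.03 to 1.4% wider, for z from the boundary to 3.5.
- Stagewise ordering, final look: the lower limit is exactly 1 when z equals the critical value, so interval and test agree. The width is 0.5 to 0.7% greater there and 2.5 to 3.1% greater at z = 2.5.
- Median-unbiased estimate, stop at look 2, 424 events: at the spending boundary the hazard ratio is 1.348 against 1.348 for the Cox estimate. At z = 3.5 it is 1.514 (spending) or 1.510 (classical) against 1.516.
- Repeated interval: 1.77 to 1.89 times wider at look 1 and 1.25 to 1.28 times wider at look 2.

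**The case against.** The strongest reply is that the protocol never calls its interval unadjusted. A group-sequential interval can also be computed from the Cox estimate and its standard error, and the choice of method is often left to an analysis plan, which is not shown here. Part of this stands: the ordinary interval is the plain reading, not an express statement. But section 12.4.1 is not silent. It fixes the level and the model and presents the interval as belonging to the analysis, without a qualifier. A plan that used another interval would have to read something into it.

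Three stronger readings are tempting, and the documents do not support them:
- A reader might infer that the trial's type I error is inflated. The ordinary interval excludes 1 in 5.3 to 5.5% of null trials, but the protocol ties rejection to the boundaries and nowhere says that the decision is taken from the interval.
- A reader might infer that the interval is too narrow after an early stop. At the design effect, coverage after a stop at look 2 is 97 to 98%, and a stagewise interval is almost the same width. The interval is narrow only by comparison with a repeated interval.
- A reader might point to coverage of 27% (spending) or 56% (classical) after a stop at look 1. That concerns only 3 to 6% of trials at the design effect, and a stagewise interval leaves it unchanged.

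**Conclusion.** The point holds, and it is minor. On its plain reading the stated interval belongs to a test at |z| = 1.960, while the final test uses 1.993 or 2.004. The cost is a coverage shortfall of about 0.3 to 1.6 percentage points and a chance of at most about 1.6% that interval and test disagree. The primary test is sound.

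The larger practical issue is the estimate. At 90% power more than half of trials stop early, and a stop at look 2 gives a log hazard ratio 22 to 24% too large on average. Estimates from trials that reach the final look err the other way, so the average over all trials is 7 to 8% too large.

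These figures assume information proportional to inclusions and the stated 90% power. Higher power reduces the bias but does not remove it.

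**What to change.** Amend section 12.4.1 to say:
- The primary 95% interval and a median-unbiased hazard ratio are obtained by stagewise ordering, using the boundaries of section 12.3.4 and the Cox estimate with its standard error.
- The ordinary Cox hazard ratio and 95% interval are reported as descriptive.
- Significance of the main criterion, and so the opening of the hierarchy in section 12.4.2, is judged against the boundary and not from any interval.

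Section 12.3.4 should also say whether the spending function or the classical bounds apply.

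The stagewise method restores coverage over all trials and agreement with the test, but it barely moves the hazard ratio after a stop at look 2. The report should therefore warn that an early-stop estimate tends to be too large. A bias-adjusted mean estimate could be added: at the look 2 spending boundary it divides the log hazard ratio by about 1.07, which takes 1.348 to exp(0.2986/1.07) = 1.32.

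The cost is a few sentences and an interval that is slightly wider, by under 1% at the final critical value and about 3% at z = 2.5. A simpler option for the final look alone is a 95.4 to 95.5% Cox interval, about 2% wider. A repeated interval is valid but much more conservative, at 1.25 to 1.9 times the width after an early stop. Sample size and conduct do not change.
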